### **6.1 DETERMINATION OF SAMPLE SIZE**

Sample size of the dose escalation study is based on the mCRM-EWOC design and not based on statistical power calculations. A minimum of 9 evaluable patients and approximately 30–50 evaluable patients will be enrolled for dose-escalation.

A simulation study has been conducted to evaluate the sample size (see Table 3 in [Appendix 11](#)). Approximately 30 patients may be enrolled in the expansion cohort to better characterize PK, PD, and preliminary activity signals at the presumed RP2D.

A sample size of thirty patients is a reasonable size for the expansion cohort in order to obtain an estimate of the response rate; with a sample size of 30 and an observed response rate of 20%, the 90% confidence interval for the true response rate is (8%, 32%), corresponding with 2 and 10 responses, and the expected number of responses is 6.

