## **6. STATISTICAL CONSIDERATIONS AND ANALYSIS PLAN**

No formal hypothesis testing is planned. Descriptive statistics will be used to summarize the safety, tolerability, pharmacokinetics, and clinical activity of RO7297089. Data will be described and summarized as warranted by number of patients in question. Listings will be used in place of tables for small numbers of patients. All analyses will be based on the safety-evaluable population, defined as all patients who receive any amount of study drug.

Continuous variables will be summarized using means, standard deviations, median and ranges; categorical variables will be presented using counts and percentages. All summaries will be presented by dose cohort to which a patient was originally assigned.

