## **6.6 ACTIVITY ANALYSES**

Response assessment data and duration of response will be summarized for all patients by cohort.

Objective response is defined as a sCR, CR, VGPR, or PR as determined by investigator assessment using IMWG response criteria. Patients with missing or no response assessments will be classified as non-responders. The objective response rate will be summarized for patients receiving the recommended Phase II dose.

Among patients with an objective response, duration of response will be defined as the time from the initial objective response to the time of disease progression or death. If a patient does not experience disease progression or death before the end of the study, duration of response will be censored at the day of the last tumor assessment. If no tumor assessments were performed after the time of first objective response, duration of response will be censored at the time of first objective response.

OS is defined as the time from the first day of study treatment (Day 1 of Cycle 1) to death. If a patient has not experienced death, OS will be censored at the day of last contact. Preliminary OS data may be tabulated and summarized using time-to-event analyses for patients receiving the RP2D.

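### The 90% confidence interval of (8%, 32%) supporting the 30-patient expansion is an unnamed Wald interval that falls short of 90% coverage at n = 30, and both its limits are too low

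*Combined protocol and SAP*

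**What the plan says.** Section 6.1 (Determination of Sample Size) gives PK, PD and preliminary activity as reasons for about 30 expansion patients. It then says: "A sample size of thirty patients is a reasonable size for the expansion cohort in order to obtain an estimate of the response rate". The numerical support follows in the same sentence: for 30 patients with a 20% observed rate, "the 90% confidence interval for the true response rate is (8%, 32%), corresponding with 2 and 10 responses". That sentence also puts the expected count at 6. The synopsis repeats this under the same heading. Neither place names the interval method or says whether it is two-sided.

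Section 6.6 (Activity Analyses) says only: "The objective response rate will be summarized for patients receiving the recommended Phase II dose". It schedules no confidence interval. Section 6 opens with: "No formal hypothesis testing is planned".

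**The concern.** This interval is the only number in Section 6.1 that shows how precisely 30 patients would estimate the response rate. A reader takes it to have 90% confidence and to exclude true rates above 32% when 6 of 30 respond. At this sample size and response rate the normal approximation is weak. If the interval is a Wald interval, its real coverage may fall below the stated level and its position may be shifted. What is at stake is whether the stated precision is accurate, and whether a reader can tell which method produced it.

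**Working it through.** **Inputs (Section 6.1).** n = 30; observed rate p = 0.20, so x = 6; confidence 90%. Two-sided is an assumption, supported by the match in step 1. It gives 5% per tail and z = 1.6449.

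**1. Reproduce the plan's figure.** Wald: p ± z·√(p(1 − p)/n).
- √(0.20 × 0.80/30) = 0.0730
- 1.6449 × 0.0730 = 0.1201
- Limits: 0.0799 and 0.3201, which round to (8%, 32%)

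None of the other variants tried gives (8%, 32%): Wald with continuity correction (6.3%, 33.7%), Agresti-Coull (10.5%, 34.5%), Jeffreys (10.3%, 33.8%), mid-P (10.0%, 34.1%), uniform-prior posterior (11.1%, 34.7%), 95% Wald (5.7%, 34.3%), 80% Wald (10.6%, 29.4%), or either method in step 3.

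**2. The response counts.** 30 × 0.0799 = 2.40 and 30 × 0.3201 = 9.60, which round to 2 and 10.

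**3. Alternatives for 6/30, two-sided 90%.**
- Exact (Clopper-Pearson): the lower limit solves P(X ≥ 6) = 0.05 and the upper limit solves P(X ≤ 6) = 0.05.
- Wilson: [p + z²/2n ± z·√(p(1 − p)/n + z²/4n²)] / (1 + z²/n), with z² = 2.7055. The centre is (0.2000 + 0.0451)/1.0902 = 0.2248 and the half-width is 0.1177.

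| Method | Lower | Upper | Width (points) | Limits × 30 |
|---|---|---|---|---|
| Wald (printed) | 8.0% | 32.0% | 24.0 | 2.4, 9.6 |
| Exact | 9.1% | 35.7% | 26.6 | 2.7, 10.7 |
| Wilson | 10.7% | 34.3% | 23.5 | 3.2, 10.3 |

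**4. Tail probabilities at the printed limits (binomial, n = 30; nominal 5% each).**
- True rate 32%: P(X ≤ 6) = 11.0%
- True rate 8%: P(X ≥ 6) = 2.9%

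The upper tail is more than twice its nominal size and the lower tail is too small, so the interval sits too low at both ends. For comparison, P(X ≤ 6) at the exact upper limit of 35.7% is 5.0%.

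**5. Coverage at a true rate of 20%.** The Wald interval contains 0.20 only when x is 4 to 10. At x = 3 its upper limit is 19.0%; at x = 11 its lower limit is 22.2%.
- P(X ≤ 3) = 12.3% (true rate above the upper limit)
- P(X ≥ 11) = 2.6% (true rate below the lower limit)
- Coverage = 100 − 12.3 − 2.6 = 85.2% (from unrounded values)

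| Method | Coverage at 20% | True rate above upper limit | Mean coverage, 8% to 32% | Minimum there | Share of range below 90% |
|---|---|---|---|---|---|
| Wald | 85.2% | 12.3% | 86.6% | 73.7% | 87% |
| Exact | 93.0% | 4.4% | 94.1% | 91.2% | 0% |
| Wilson | 89.5% | 4.4% | 90.1% | 82.6% | 56% |

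The last three columns use an evenly spaced grid of 24,001 true rates from 8% to 32%. Coverage moves up and down because the data are discrete; at a true rate of 19%, for example, Wald covers about 90%.

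**The case against.** The strongest reply is that the interval is an illustration. Section 6.1 poses a what-if about an observed 20%. No hypothesis test is planned, Section 6.6 commits only to summarizing the response rate, and the futility rule in Section 6.8 uses a Bayesian posterior with a uniform prior. Its 25% threshold lies inside all three intervals. Long-run Wald coverage therefore describes a procedure that the plan does not schedule. All of this stands and limits the consequence. It does not make a figure labelled 90% into a 90% interval.

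The second reply is that the alternatives are not perfect. Wilson is itself below 90% over 56% of the range examined, and exact is conservative, averaging 94.1%. The 3.7-point shift in the upper limit depends on choosing exact; against Wilson it is 2.2 points, less than one patient in 30. That also stands. But Wilson averages close to the nominal level and exact never falls below it, while Wald falls short on average and at the planning value.

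A reader might go further in three ways that the documents do not support.
- **Arithmetic error.** The stated inputs give the stated output; the weakness is the method and the missing name.
- **Wrong response counts.** 2/30 = 6.7% and 10/30 = 33.3% do fall just outside the printed limits, but this comes only from converting rounded counts back to percentages.
- **Thirty patients is unsupported.** The printed width of 24.0 points lies between Wilson (23.5) and exact (26.6), so the claim that 30 is a reasonable size is unaffected.

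**Conclusion.** The point holds as a minor correction. The printed (8%, 32%) is a Wald interval whose actual coverage is 85.2% at a true 20% and 86.6% on average over true rates of 8% to 32%, against a stated 90%. Its lower limit is too low by 1.1 points (exact) or 2.7 points (Wilson), and its upper limit by 3.7 or 2.2 points. In particular, true rates between 32% and 35.7% appear excluded by 6/30, but the exact interval does not exclude them.

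This rests on reading the interval as two-sided and on a binomial count in 30 patients. A reader might also infer that the final response rate will be reported with a Wald interval. The plan does not say so: Section 6.6 specifies no interval at all. No decision rule or planned analysis uses the printed figure.

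**What to change.** In Section 6.1 and in the synopsis, replace (8%, 32%) with the exact (Clopper-Pearson) 90% interval, (9%, 36%), and name the method. Exact is suggested because its coverage is at least 90% at every true rate. Wilson, (11%, 34%), would be an acceptable alternative if narrower limits and near-nominal average coverage are preferred. Drop the two response counts, or update them to match the new limits (exact: 2.7 and 10.7 of 30). If an interval for the observed response rate is to be reported, name the same method in Section 6.6.

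The cost is a wording change in two places. The exact interval is 2.6 points wider than the printed one (unrounded widths 26.61 and 24.02). Both limits rise: the lower from 8% to 9% and the upper from 32% to 36%. The sample size, the Section 6.8 interim rules and the planned analyses stay as they are.

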### **6.2 SUMMARIES OF CONDUCT OF STUDY**

The number of patients who enroll, discontinue, or complete the study will be summarized. Reasons for premature study discontinuation will be listed and summarized. Enrollment and major protocol deviations will be listed and evaluated for their potential effects on the interpretation of study results. The study is open-label; therefore, no blinded treatment will be administered. Patients will be assigned to a dose/regimen rather than randomized.

### **6.3 SUMMARIES OF DEMOGRAPHIC AND BASELINE CHARACTERISTICS**

Demographic and baseline characteristics (including age, sex, race and ethnicity, weight, and disease characteristics such as duration of malignancy) will be summarized using means, standard deviations, medians, and ranges for continuous variables and proportions for categorical variables, as appropriate. Summaries will be presented overall and by originally assigned dose level.

## 6.4 SAFETY ANALYSES

The primary objective for this study is to evaluate the safety of RO7297089, including estimation of the MTD and characterization of DLTs, on the basis of the following endpoints:

- Nature, frequency, severity, and timing of adverse events, including DLTs
- Changes in vital signs, physical findings, and clinical laboratory results during and following RO7297089 administration

The safety analysis population will consist of all patients who received at least one dose of study drug. Statistical summaries will be descriptive in nature (e.g., incidence rates, means, and percentiles).

### Primary Safety Model (mCRM-EWOC)

An mCRM-EWOC model will be utilized to inform decision-making about the dose of RO7297089. All patients will be followed through the DLT window (*14 days; see Figure 2*) and be enrolled in a sequential manner. Patients within a cohort will be sequentially enrolled in cohorts of three patients each, which, if required, can be expanded with additional patients.

The dose-toxicity relationship will be described by a two-parameter logistic regression model, which can be updated anytime by incorporating available information from all patients. A minimal informative prior will be used.

The Sponsor and Investigators will evaluate the next dose recommended by the mCRM-EWOC design and agree on the dose for the subsequent cohort. At each dose-escalation step, the dose can be escalated, de-escalated, or an additional cohort at that same dose level could be enrolled.

The mCRM will continue until a maximum of approximately 40 patients, or all rules in a pre-defined set of MTD precision criteria, have been reached; or if it is concluded that the RP2D has been defined, using multiple parameters of safety, PD, and efficacy data.

The set of MTD precision criteria is:

- At least 9 patients have accrued overall;
- At least 6 patients have been accrued near the MTD dose where “near” is defined as being within 20% of the MTD;
- The probability that the MTD lies within the target toxicity interval is above 40%.

After the dose-escalation phase, a tentative RP2D, which will guide the recommended dose in expansion, will be defined. The final RP2D will be estimated based on the DLT occurrence rate in all patients evaluable for DLTs in the dose-escalation and dose-expansion parts of the study. The model will be implemented by R and Jags software.

All patients from the safety analysis population who follow the protocol-specified dose regimen within the DLT observation period and have undergone the scheduled safety evaluations, or who discontinued earlier due to a DLT, will be included in the MTD-determined analysis.

Clinical judgment can always override the Bayesian adaptive design recommendations in the dose-selection process.

#### **6.4.1            Analyses of Exposure, Adverse Event, Laboratory, and Vital Sign Data**

Safety will be assessed through summaries of exposure to study treatment, adverse events, changes in laboratory test results, and changes in vital signs and ECGs.

Study treatment exposure (such as treatment duration, total dose received, and number of cycles and dose modifications) will be summarized with descriptive statistics.

All verbatim adverse event terms will be mapped to Medical Dictionary for Regulatory Activities (MedDRA) thesaurus terms, and adverse event severity will be graded according to NCI CTCAE v5.0. All adverse events, serious adverse events, adverse events leading to death, adverse events of special interest, and adverse events leading to study treatment discontinuation that occur on or after the first dose of study treatment (i.e., treatment emergent adverse events) will be summarized by mapped term, appropriate thesaurus level, and severity grade. For events of varying severity, the highest grade will be used in the summaries. Deaths and cause of death will be summarized.

Relevant laboratory, vital sign (pulse rate, respiratory rate, blood pressure, and temperature), and ECG data will be displayed by time, with grades identified where appropriate. Additionally, a shift table of selected laboratory tests will be used to summarize the baseline and maximum post-baseline severity grade. Changes in vital signs and ECGs will be summarized.

### **6.5                PHARMACOKINETIC ANALYSES**

Individual and mean serum RO7297089 concentration versus time data will be tabulated and plotted. The serum pharmacokinetics of RO7297089 will be summarized by estimating the following:

- AUC
- $C_{max}$
- $t_{max}$
- $C_{min}$
- Total clearance
- Volume of distribution at steady state

- Half-life (as appropriate for data collected)

Compartmental, non-compartmental, and/or population methods may be considered. Estimates for these parameters will be tabulated and summarized (mean, standard deviation, coefficient of variation, median, minimum, and maximum), as appropriate. Additional PK analyses may be conducted as appropriate.

## **6.6 ACTIVITY ANALYSES**

Response assessment data and duration of response will be summarized for all patients by cohort.

Objective response is defined as a sCR, CR, VGPR, or PR as determined by investigator assessment using IMWG response criteria. Patients with missing or no response assessments will be classified as non-responders. The objective response rate will be summarized for patients receiving the recommended Phase II dose.

Among patients with an objective response, duration of response will be defined as the time from the initial objective response to the time of disease progression or death. If a patient does not experience disease progression or death before the end of the study, duration of response will be censored at the day of the last tumor assessment. If no tumor assessments were performed after the time of first objective response, duration of response will be censored at the time of first objective response.

OS is defined as the time from the first day of study treatment (Day 1 of Cycle 1) to death. If a patient has not experienced death, OS will be censored at the day of last contact. Preliminary OS data may be tabulated and summarized using time-to-event analyses for patients receiving the RP2D.

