## 2.3 ACTIVITY OBJECTIVES

The activity objective for this study is to make a preliminary assessment of the activity of RO7297089 on the basis of the following endpoints:

- Objective response rate (ORR), defined as a stringent complete response (sCR), complete response (CR), very good partial response (VGPR), or partial response (PR), as determined by the investigator according to International Myeloma Working Group (IMWG) Uniform Response Criteria ([Appendix 5](#))
- Duration of response (DOR), defined as the time from the first occurrence of a documented objective response to disease progression or death from any cause (whichever occurs first), as determined by the investigator according to IMWG Uniform Response Criteria

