### **4.6 TREATMENT, PATIENT, STUDY, AND SITE DISCONTINUATION**

#### **4.6.1 Study Treatment Discontinuation**

Patients must permanently discontinue study treatment if they experience any of the following:

- Any medical condition that the investigator or Sponsor determines may jeopardize the patient's safety if he or she continues to receive study treatment
- Investigator or Sponsor determination that treatment discontinuation is in the best interest of the patient
- Pregnancy
- Use of an anticancer therapy not required per protocol
- Symptomatic deterioration attributed to disease progression
- Confirmed disease progression per investigator assessment according to IMWG Uniform Response Criteria ([Appendix 5](#))
- Patient decision

The primary reason for study treatment discontinuation should be documented on the appropriate eCRF. Patients who discontinue study treatment prematurely will not be replaced unless enrolled in the dose-escalation cohorts and discontinue prior to completion of the 14-day DLT assessment window.

Patients will return to the clinic for a treatment discontinuation visit 30 ( $\pm$  10) days after the final dose of study drug (see [Appendix 1](#) for additional details). Additionally, patients who discontinue study treatment for reasons other than documented disease progression or relapse should continue to be followed as described in [Appendix 2](#) until disease progression, start of new anti-cancer therapy, or withdrawal from study participation, whichever occurs first.

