#### **4.6.1.1 Survival and Subsequent Anti-Cancer Therapy Follow-Up**

Following study treatment discontinuation (initial or after re-treatment), patients may be followed for survival and subsequent anti-cancer therapy. Survival and subsequent anti-cancer therapy follow-up information may be collected via telephone calls, patient medical records, and/or clinic visits approximately every 3 months until death, loss to follow-up, or study termination by the Sponsor unless the patient requests to be withdrawn from follow-up. Information on subsequent anti-cancer therapies will include systemic therapies (e.g., chemotherapy, targeted therapy, hormonal therapy), surgery (e.g., resection of metastatic disease), and radiation procedures (radiotherapy to a tumor lesion). If the patient withdraws from the study, the site's staff may use a public information source (e.g., county records) to obtain information about survival status only.

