## Appendix 2 Schedule of Activities: Post-Treatment Follow-Up

Assessments/Procedures	Post-Treatment Follow-Up a
Targeted physical examination b	Every 3 months
Vital signs (blood pressure, pulse rate, and body temperature)	Every 3 months
ECOG Performance Status	Every 3 months
Tumor assessments including SPEP with SIFE and SFLCs performed centrally; UPEP with UIFE and imaging performed locally as clinically indicated	Every 3 months
Total IgA, IgG, IgM	Every 3 months
Hematology c	Every 3 months × 2, then every 6 months
Serum chemistry d	Every 3 months × 2, then every 6 months
Bone marrow biopsy and aspirate e	As needed to confirm relapse

ADA = anti-drug antibody; ECOG = Eastern Cooperative Oncology Group; eCRF = electronic Case Report Form; PK = pharmacokinetic; SFLC = serum free light chain; SIFE = serum immunofixation electrophoresis; SPEP = serum protein electrophoresis; UIFE = urine immunofixation electrophoresis; UPEP = urine protein electrophoresis.

- a Schedule corresponds to visit timepoints only for patients who do not discontinue the study due to progressive disease. Perform assessments until disease progression, start of new anti-cancer therapy, or withdrawal from study participation, whichever occurs first. Continue to follow patients on this schedule timed from the treatment termination visit 30 days ( $\pm 10$  days) after the last dose of RO7297089 administered. The first 2 visits should occur within  $\pm 7$  days from the scheduled date, while subsequent visits should occur within  $\pm 14$  days from the scheduled date.
- b Targeted physical examinations should be limited to systems of primary relevance (i.e., cardiovascular, respiratory, neurologic, and any system that might be associated with tumor assessment [e.g., those systems associated with symptoms], or potential drug-related toxicity; see Section 5.1.1). Changes from baseline abnormalities should be recorded in patient notes. New or worsened clinically significant abnormalities should be recorded as adverse events on the Adverse Event eCRF.
- c Hematology includes WBC count, RBC count, hemoglobin, hematocrit, platelet count, and differential count (neutrophils, eosinophils, basophils, monocytes, lymphocytes, other cells [if present]).

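### Duration of response counts a death after new anti-cancer therapy as an event, although scheduled tumor assessments stop when that therapy starts

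*Combined protocol and SAP*

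**What the plan says.** All references are to the combined protocol and SAP.

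- **Event.** Section 2.3 measures DOR "from the first occurrence of a documented objective response to disease progression or death from any cause (whichever occurs first"), as judged by the investigator. Section 6.6 agrees: "duration of response will be defined as the time from the initial objective response to the time of disease progression or death". Neither limits when the death may occur.
- **Censoring.** Section 6.6 has two rules. The first is "If a patient does not experience disease progression or death before the end of the study, duration of response will be censored" on the day of the last tumor assessment. The second censors a responder who has no later tumor assessment on the date of the first response. Neither mentions new anti-cancer therapy.
- **When assessments stop.** Under Section 4.6.1, patients who stop study drug without progression are followed "until disease progression, start of new anti-cancer therapy, or withdrawal from study participation, whichever occurs first". Appendix 2 repeats this for the scheduled assessments: "Perform assessments until disease progression, start of new anti-cancer therapy, or withdrawal from study participation, whichever occurs first".
- **New therapy ends study drug.** Section 4.6.1 lists "Use of an anticancer therapy not required per protocol" among the reasons for permanent discontinuation.
- **Deaths after that.** Under Section 4.6.1.1 patients may be followed for survival and later therapy "approximately every 3 months until death, loss to follow-up, or study termination by the Sponsor". Section 5.6 asks for all deaths after the adverse event period to be reported, whatever the cause.

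Appendix 5 does use the start of new therapy as a limit, but only for confirming a response. It does not govern how long a response is counted.

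**The concern.** The definition and the data collection do not match. Once a responder starts another drug, the plan can still record a death but has no scheduled way to record progression. If that patient dies before study end, Section 6.6 treats the whole interval from last assessment to death as time in response, although nobody was checking the response and the patient was on a different treatment.

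The rule also separates patients on a fact that says little about the response. Take two responders with the same history who stop without progression and start the same next drug. The one alive at study end is censored at the last tumor assessment. The one who dies has an event at death, possibly months later, and so has the longer recorded DOR.

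DOR is one of the two activity endpoints in Section 2.3, and activity data feed into the choice of recommended Phase II dose (Sections 2.6 and 3.1.1.2). With few responders, individual values carry weight.

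**Working it through.** The plan states no DOR figure, so there is none to reproduce. The check traces one patient through the rules and then shows the effect on a small group.

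**1. Size of the DOR set.** Section 6.1 assumes 30 expansion patients and a 20% response rate.

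- Expected responders: 0.20 × 30 = 6, as stated.
- Wald 90% interval: 0.20 ± 1.645 × √(0.20 × 0.80 / 30) = 0.20 ± 0.120, or 7.99% to 32.01%. This matches the stated 8% to 32%.
- One patient of six is 1/6, about 17%.

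**2. One patient through the rules.** Assumed, in months from first response: last tumor assessment at month 3, no progression, then another drug.

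- Alive at study end: the first censoring rule applies, and DOR is censored at month 3. The schedule places the last assessment at or before the switch, so no time on the next drug is counted.
- Dies before study end: the first censoring rule no longer applies, and DOR is an event at death.

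Against censoring at month 3, the recorded time is longer by:

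- death at 4.5: 4.5 − 3 = 1.5 months
- death at 9: 9 − 3 = 6 months
- death at 15: 15 − 3 = 12 months

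**3. Group estimate.** Assume six responders: five with events at months 2, 4, 6, 8 and 10, and the patient above. The Kaplan-Meier estimate is S(t) = ∏(1 − d/r), with d events among r at risk.

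- Censored at month 3: after month 6, 5/6 × 3/4 × 2/3 = 0.42; after month 8, × 1/2 = 0.21.
- As written, death at 9 or 15: after month 6, 5/6 × 4/5 × 3/4 = 0.50; after month 8, × 2/3 = 0.33.
- As written, death at 4.5: after month 4.5, 5/6 × 4/5 × 3/4 = 0.50; after month 6, × 2/3 = 0.33; after month 8, × 1/2 = 0.17.

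| Rule | S after month 6 | S after month 8 | Median |
|---|---|---|---|
| Censored at month 3 | 0.42 | 0.21 | 6 |
| As written, death at 4.5 | 0.33 | 0.17 | 4.5 |
| As written, death at 9 | 0.50 | 0.33 | 6 |
| As written, death at 15 | 0.50 | 0.33 | 6 |

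The median is the first time S is 0.5 or less. If it is instead read as the midpoint of the flat stretch at exactly 0.50 (months 6 to 8), the last two rows give 7. A late death raises the curve at months 6 and 8. An early death lowers it, because an early censoring has become an early event.

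**The case against.** **The effect is narrow.** Only a responder who switches without documented progression and whose recorded death precedes study end is affected. Section 4.4.3 generally bars other cancer therapy until progression is documented and study drug has stopped, which makes such switches less usual, although Section 4.6.1 foresees them. The documents give no frequency. This stands and sets the scope of the point.

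**Capture of deaths is uncertain.** Section 4.6.1.1 says patients may be followed for survival, so follow-up is optional. This stands, but Section 5.6 still asks for later deaths to be reported. Study end is expected about 1 year after the last enrollment (Section 3.2), so some deaths can be captured.

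**The rule may be deliberate.** Counting death regardless of later therapy is a recognizable treatment-policy approach. However, that approach also needs progression to be followed after the switch, and the plan stops the scheduled assessments there. The planned data cannot support it.

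**Censoring at a switch has its own weakness.** The decision to switch may be informative about prognosis. This stands and is the reason for the sensitivity analyses. Censoring at new therapy also does not address a death after a long assessment gap with no new therapy.

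**Little depends on DOR.** Section 6 plans no hypothesis test and uses listings for small numbers, and expansion futility in Section 6.8 uses the response rate. This also stands.

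A reader might infer that the rule inflates the median DOR, or credits RO7297089 at group level with the effect of the next drug. The documents do not support that: patients alive at study end are already censored properly, and the direction of the group effect depends on when the death occurs.

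**Conclusion.** The gap is real and limited. Followed exactly, Section 6.6 gives a responder who switches therapy without documented progression, and whose death is then recorded, an event at death after an unassessed interval on another drug. No other section closes this. The recorded DOR for that patient is lengthened, by 1.5 to 12 months in the assumed cases. The Kaplan-Meier median can fall, stay the same or, under the midpoint convention, rise. One such patient would be about 17% of the roughly 6 responders expected in expansion.

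These conclusions rest on the plan's 20% response rate and on assumed event times. How many patients would be affected cannot be estimated from the documents. Because DOR is descriptive and no decision rule uses it, this is a cheap improvement. It is worth settling before responder data are seen, since with so few responders a later choice of rule could change the reported result.

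**What to change.** Add to Section 6.6: *Responders who start new anti-cancer therapy before documented progression are censored at the last tumor assessment on or before the start of that therapy. One sensitivity analysis uses the current rule (death at any time counts as an event), and one counts new therapy as an event.*

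Record the start date of new therapy explicitly. Section 4.6.1.1 lists types of later therapy but does not name the date, so it should not be assumed to be collected, even though the cut-offs in Sections 4.6.1 and 5.3.1 depend on it.

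The cost is this text, one date field if it is not already there, and two small sensitivity summaries. A little DOR follow-up is given up, and censoring at a switch may be informative. The sensitivity analyses show how much either matters.
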